9.1.1.3 Definition of Parasite Clearance (by Microscopy)

A blood film will be considered 'negative' when the examination of 1000 white blood cells reveals no asexual parasites (see the study operational manual for more detail). Parasite clearance time is defined as the time of the first negative film, to be confirmed with a second negative film prepared within 6 to 12 hours of the first one. Parasite clearance will be concluded following confirmation of the second negative film.

If parasites have not cleared by 72 hours after IMP administration and criteria for rescue medication are not met at 72h, blood films should continue to be taken according to site standard practice (or at minimum every 8 hours) until parasite clearance is shown or until criteria for rescue medication are met (see Section 7.7.1).

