9.1.1.4 Quantitative PCR, parasite genotyping analysis

Blood samples to measure parasitemia by qPCR will be taken according to SoA; qPCR analysis will be performed by the testing laboratory at all scheduled time points.

Blood samplings for genotyping will be collected according to SoA and at the time-points when recrudescence or re-infection after initial parasite clearance was shown on the blood slide. Parasite genotyping analysis will be performed by the testing laboratory on previously collected blood spot sample only in case of a positive blood film after initial parasite clearance: one pre-dose sample and one sample at 18 or 24 hours post dosing. A further sample will be analyzed at the time point at which recrudescence/re-infection occurs.

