
- Development of danger signs or symptoms of complicated/severe malaria on Day 1, Day 2 or Day 3, in the presence of parasitemia (reported as Term='Complicated Malaria' by the investigator in the 'Adverse Event' form and reported in the e-CRF dedicated form "Malaria Signs and Symptoms") concomitant to at least one positive parasitemia. Considering that the drug cannot be active before 24h, a severe malaria presenting between 0h and 24h is highly suspect of wrong inclusion of the patient.- Parasitemia on Day 2 higher than baseline parasitemia count (irrespective of body temperature)- Parasitemia on Day 3 with axillary temperature of $\geq 37.5^{\circ}\text{C}$- Parasitemia on Day 3 $\geq 25\%$ of baseline parasitemia count
LCF is defined as one of the following, without previously meeting any of the ETF criteria :

- Development of danger signs or severe malaria after Day 3 in the presence of parasitemia (reported as Term='Complicated Malaria' by the investigator in the 'Adverse Event' form and reported in the e-CRF dedicated form "Malaria Signs and Symptoms") concomitant to at least one positive parasitemia.- Presence of parasitemia and axillary temperature $> 37.5^{\circ}\text{C}$ on any day from Day 4 to Day 28, without previously meeting any of the criteria of early treatment failure
LPF

- Presence of parasitemia on any day from Day 7 to Day 28, and axillary temperature $< 37.5^{\circ}\text{C}$, without previously meeting any of the criteria of ETF or LCF

Criterion

ACPR

- Absence of parasitemia on Day 28 irrespective of axillary temperature without previously meeting any of the criteria of ETF or LCF or LPF, and without previous rescue therapy start. Rescue therapy start without previous WHO criteria can be due to: investigator decision (classified as failure or deviation based on case by case clinical review, see [Section 2.3.2.2](#)), major vomiting or severe malaria at Day 0 (both classified as deviation, see [Section 2.3.2.2](#)), other species infection.

The following definitions will also be considered regarding efficacy evaluation:

Re-emergence / Recurrence (recrudescence and re-infection): The appearance of asexual parasites after clearance of initial infection irrespective of genotype.

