Recrudescence: The appearance of asexual parasites after clearance of initial infection with a genotype identical to that of parasites present at baseline. Recrudescence is confirmed by microscopy (positive blood smear) and by genotyping PCR analysis.

Re-infection: The appearance of asexual parasites after clearance of initial infection with a genotype that differs from that of parasites present at baseline. Re-infection is confirmed by microscopy (positive blood smear) and by genotyping PCR analysis.

Treatment failure: Any patients who met any of the criteria for ETF, LCF or LPF.

Crude ACPR does not distinguish between re-infection (by a new clone of parasite) and recrudescence (re-emergence of the original clone of parasite that was present at baseline); i.e. presence of either a new clone or genotypically identical parasite will be considered a treatment failure.

PCR-corrected ACPR applies only to recrudescence; (i.e. patients with re-infection are considered non-evaluable for the analysis of PCR-adjusted ACPR). Presence of a genotypically identical parasite will be considered a treatment failure.

Genotyping adjustment

LCF occurring from Day 7 or LPF will be sub-classified as follows using parasite genotyping results:

- *P. falciparum* recrudescence, if no other species reported in eCRF and genotyping result is “recrudescence”
- *P. falciparum* reinfection, if no other species reported in eCRF and genotyping result is “reinfection”

- Other species with *P. falciparum* recrudescence, if other species reported in eCRF and genotyping result is “recrudescence”
- Other species with *P. falciparum* reinfection, if other species reported in eCRF and genotyping result is “reinfection”
- Undetermined, negative or missing PCR, if genotyping result is “Undetermined”, “negative”, “undetermined” or “missing”, with or without other species infection.

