2.1.4.1 Primary efficacy endpoint

The primary efficacy endpoint is the PCR-corrected ACPR at Day 28. The PCR-corrected ACPR at Day 28 will be derived from the efficacy evaluation at Day 28 defined as follows:

Efficacy evaluation at Day 28	Per Protocol	miITT
	PCR-corrected ACPR at Day 28	PCR-corrected ACPR at Day 28
ACPR	Success	Success
ETF	Failure	Failure
LCF before Day 7	Failure	Failure
LCF on or after Day 7 or LPF		
- P. falciparum recrudescence	Failure	Failure
- P. falciparum reinfection prior to Day 28	Excluded from analysis	Failure
- P. falciparum reinfection on Day 28	Success	Success
- Other species mixed with P. falciparum recrudescence	Failure	Failure
- Other species mixed with P. falciparum reinfection	Excluded from analysis	Failure
- Undetermined, negative or missing PCR	Excluded from analysis	Failure
Rescue therapy start without previous ETF, LCF, LPF, or other species infections, and not classified as a protocol violation	Before Day 7: Failure On/after Day 7: excluded from analysis	Failure
Other species infection without P. falciparum reemergence	Excluded from analysis	Failure
Lost to follow-up	Excluded from analysis	Failure
Withdrawal*	Excluded from analysis	Failure
Protocol violation**	Excluded from analysis	Failure

(*): Patient's request - Investigator's judgement - Adverse event - Other

(**): protocol violations potentially impacting efficacy assessment at Day 28 for the PP population as defined in [Section 2.3.2.2](#)

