2.1.4.2.4 Re-emergence time

Timing to consider

In this section, except otherwise specified, the post-dose timing associated to parasitemia will refer to:

- its assigned time point as defined in [Section 2.5.4.1](#), if it exists,
- its actual post-dose timing as defined in [Section 2.5.4.1](#) and expressed in days, if outside defined time windows.

Establishing re-emergence

The re-emergence is defined as the re-appearance of asexual forms of *P. falciparum* irrespective of genotype after clearance of initial infection. Blood thick films performed before Hour 24 (Day 1) time point will not be considered for re-emergence screened.

Time to re-emergence

The time to re-emergence will be the post-dose timing associated to the first positive - observed or imputed - parasitemia after clearance. For patient not reaching parasite clearance of initial infection, the time to re-emergence will be equal to zero.

In patients having reach parasite clearance of initial infection, in case a rescue therapy would be started without previous re-emergence or other species infection, then the time to re-emergence will be the time point of the rescue therapy start. If the case has been classified as a protocol violation, then the time to re-emergence will be censored at the time of the rescue start.

Otherwise, the time to re-emergence will be censored at the post-dose timing associated to the last available patient's thick film before withdrawn (for any reason), or, on/before start of a rescue therapy for other species infection, whichever comes first.

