- e Local thick and thin blood films performed at the site, before Informed Consent signature, according to local standard procedures and within 4 hours prior to dosing, can be used as screening/ pre-dose parasitemia assessments ([Section 9.1.1.1](#) of protocol) provided that a standard procedure is in place at site and blood films staining is performed according to the study operational manual. Blood films (thick and thin) and temperature measurements need to be confirmed as follows: when 1st parasite clearance and 1st temperature < 37.5 °C, measurements need to be confirmed with second reading 6 to 12 hours after the first measurement (ie, to determine Parasite Clearance and Fever Clearance). The first measurement (if confirmed) will be considered the 'Clearance Time'. Asexual and sexual counts will be measured separately: only asexual count will be used as parasitemia for evaluation of study endpoints. If parasites have not cleared within 72 hours after IMP administration and criteria for rescue medication are not met at 72 hours post-dose, blood films should continue to be taken according to site standard practice (or at minimum every 8 hours) until parasite clearance is shown or until criteria for rescue medication are met (see [Section 7.7.1](#) of protocol). If these additional blood smears are taken they should be recorded as unscheduled visits in the e-CRF. Axillary temperature should be recorded, if the axillary method is not possible, an alternative route (oral, tympanic, rectal) may be used. Within an individual participant the same method of temperature measure should be used throughout the study.
- f RT-qPCR and qPCR will be performed at all parasitemia time-points (To be collected, according to the schedule and the instructions reported in the study operational manual). Parasite genotyping analysis will be performed on previously collected blood spot sample only in case of a positive blood film after initial parasite clearance: one pre-dose sample and one sample at 18 or 24 hours post dosing. A further sample will be analyzed at the time point at which recrudescence/re-infection occurs (if applicable).
- g Single local ECG reading for inclusion purpose and triplicate central ECG reading for safety evaluation during study.
- h Laboratory safety will be performed locally: hematology, clinical chemistry, and urinalysis (see [Appendix 2](#) of protocol for details).

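### Parasitemia that persists to Day 7 gets no genotype by design, so PCR-corrected ACPR drops a certain failure in the Per Protocol column and possibly in the primary model

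*Protocol*

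**What the plan says.** **Genotyping trigger.** Protocol 9.1.1.4 restricts the laboratory analysis to cases with "only in case of a positive blood film after initial parasite clearance". Footnote f of the SAP flow chart (Appendix A) repeats the condition: analysis "on previously collected blood spot sample only in case of a positive blood film after initial parasite clearance". Spots are collected at all parasitemia time points, but no rule sends them for genotyping when parasites persist.

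**Persistence is foreseen.** Protocol 9.1.1.3 provides for continued films "If parasites have not cleared by 72 hours after IMP administration and criteria for rescue medication are not met at 72h".

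**Failure definitions.** SAP 2.1.4 (Table 1) defines LPF by "Presence of parasitemia on any day from Day 7 to Day 28" without fever and without an earlier early treatment failure (ETF) or LCF. Prior clearance is not a condition.

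**Use of genotype.** Under Genotyping adjustment, SAP 2.1.4 states: "LCF occurring from Day 7 or LPF will be sub-classified as follows using parasite genotyping results". The last class, "Undetermined, negative or missing PCR, if genotyping result is" undetermined, negative or missing, takes every case without a result.

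**Coding.** In the SAP 2.1.4.1 table, "Undetermined, negative or missing PCR" is excluded in the Per Protocol (PP) column and a failure in the mITT column. SAP 2.4.4.1.2 confirms that such PP patients are not evaluable.

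**Primary population.** SAP 1.6, 2.3, 2.3.5.1 and 2.4.4 put the primary exposure-response model on the PK/PD efficacy population. None of them says which column of the 2.1.4.1 table it follows. The efficacy summary table at the end of Appendix B names PP for the same model.

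**The concern.** PCR correction exists to separate recrudescence from re-infection. SAP 2.1.4 defines both as parasites appearing after the initial infection has cleared. A patient whose films have been positive since baseline can be neither, so genotype has nothing to decide. The same section counts any LPF as a treatment failure. Excluding the patient as missing PCR treats a known failure as an unknown outcome.

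The rule also has a perverse edge. A persistent patient given rescue before Day 7 without WHO criteria, and not classed as a protocol violation, is a failure in both columns. The same patient left until Day 7 is excluded in the PP column. Longer persistence removes the failure.

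At stake are the by-arm PP cure rates in SAP 2.4.4.1.2 and possibly the primary regression. Dropping failures raises cure rates most where persisters are most frequent. It narrows the gap between arms and costs the model some of its few failures, which works against showing an OZ439 contribution.

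**Working it through.** **1. Trace of one patient through the rules**

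| Step | Source | Result |
|---|---|---|
| Day 2 count not above Day 0; Day 3 positive, below 25% of baseline, afebrile, no danger signs | Protocol 7.7.1; SAP Table 1 | Not ETF |
| Days 4 to 6 positive, no fever or history of fever, no danger signs, no rescue | Same | Not LCF |
| Day 7 positive, afebrile | Same | LPF (LCF from Day 7 if febrile) |
| No negative film so far | Protocol 9.1.1.4 | Genotyping not triggered |
| LPF must be split by genotype | SAP 2.1.4 | Missing PCR |
| PP column | SAP 2.1.4.1 | Excluded |
| mITT column | SAP 2.1.4.1 | Failure |
| PK/PD efficacy population | SAP 2.3.5.1 | Not specified |

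**2. Which column does the PK/PD efficacy population follow?** SAP 2.3.5.1 cites 2.1.4.1 for four reasons that make a patient non-evaluable: other species without *P. falciparum* re-emergence, loss to follow-up, withdrawal and protocol violation. In the table all four are excluded in the PP column and all four are failures in the mITT column. On every item it names, the population behaves like PP. Its silence on missing PCR does not decide the matter: the PP list in 2.3.2.2 has the same four items and omits missing PCR too, yet the PP column excludes it.

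**3. Effect on a by-arm rate.** Planned cure rate with FQ alone is 72% (Protocol Appendix 8), with 30 evaluable per arm: 0.72 × 30 = 21.6, taken as 22. With k persisters dropped the rate is 22/(30 − k).

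| k dropped (assumed) | Rate |
|---|---|
| 0 | 22/30 = 73.3% |
| 1 | 22/29 = 75.9% |
| 2 | 22/28 = 78.6% |
| 3 | 22/27 = 81.5% |

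**4. Effect across arms.** If a share s of failures is dropped, a cure rate p becomes p/[p + (1 − p)(1 − s)]. With s = 25% in every arm (assumed), the planned 72%, 81%, 91% and 97% become 0.72/0.93 = 77.4%, 0.81/0.9525 = 85.0%, 0.91/0.9775 = 93.1% and 0.97/0.9925 = 97.7%. The gap from FQ alone to 1000 mg shrinks from 25 to 20.3 points. The odds in each arm are multiplied by the same 1/(1 − s), so odds ratios do not change. On the logit scale the slope is attenuated only if persisters form a larger share of failures at low OZ439 exposure.

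**5. Effect on the primary model, if the exclusion reaches it.** The plan states power around 90% with 30 per arm. Simulating equation 2 of Appendix 8 (α = 3.23, βFQ = 0.12, βOZ439 = 0.73, βBasePar = −1.27, truncated-normal baseline, two-sided 5% Wald test, 2,000 trials) needs Day 7 concentration distributions that the documents do not give. Assumed: uncorrelated log-normals, FQ CV 50%, medians calibrated to 72/81/91/97%. For OZ439 CV of 30, 50, 70, 100 and 150%, power was 92.0, 94.0, 92.6, 91.8 and 85.3%. This is compatible with the stated figure but not a strict reproduction.

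At OZ439 CV 70%, with about 17.7 failures expected in 120 patients and the persister share equal in all arms:

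| Share of failures that persist (assumed) | Mean number excluded | Arm A rate if excluded (72% if counted) | Power if excluded | Power if counted |
|---|---|---|---|---|
| 10% | 1.8 | 74% | 90% | 94% |
| 25% | 4.4 | 77% | 80% | 94% |
| 50% | 8.8 | 84% | 46% | 94% |

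By step 4, the loss of power in this equal-share setting comes from having fewer failures, not from a flatter slope.

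**The case against.** **Scope.** The mITT column is already right. The primary population is built from mITT, and its list does not name missing PCR. SAP 2.4.4 puts the dose-response analysis on mITT, and the PP frequency table appears beside an mITT one that shows the difference. This stands as a limit on the point. It does not show that the primary model is safe, because the four cited exclusions contradict the mITT column.

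**Self-contradiction.** A reader might infer that the SAP contradicts itself, since SAP 2.1.4.2.4 says "For patient not reaching parasite clearance of initial infection, the time to re-emergence will be equal to zero" and time to recrudescence inherits that event. The documents do not support this. SAP 2.4.4.2 runs those endpoints on mITT, where PCR-corrected ACPR also counts the patient as a failure. A conflict arises only if the Appendix B summary table, which lists PP throughout, is taken over the body text.

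**Rarity.** The patient must escape every ETF and early LCF criterion while films continue at least every 8 hours, and must receive no rescue before Day 7. This is a narrow case, and the documents give no count.

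**Misclassification by the remedy.** Coding every failure without confirmed clearance as Failure would go too far. Under SAP 2.1.4.2.3, two negative films spaced outside 6 to 12 hours followed by a positive third film invalidate clearance. That third film could be a true re-infection. This objection stands, and the fix is limited accordingly.

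**Direction.** The distortion works against the sponsor's hypothesis and would not create a false claim. That lowers the stakes, but a coding rule for the primary endpoint should still be settled before database lock.

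**Conclusion.** The gap is real. By stated rule, a patient with continuously positive films who first fails on or after Day 7 has no genotype and is excluded from PP PCR-corrected ACPR, although the outcome is certain. The mITT coding is correct.

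A reader might infer that the primary analysis definitely loses these failures. The documents do not go that far. The column for the PK/PD efficacy population is unstated; exclusion is the better-supported reading, not an established one.

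The size cannot be fixed from the documents. Dropping 1 to 3 persisters would move a 73.3% rate to 75.9% to 81.5%. It is tempting to read the last figure as FQ alone catching up with the 81% planned for 300 mg, but the same rule would remove persisters from that arm too. Differences in cure rate shrink even with an equal persister share in every arm; odds ratios shrink only if that share is higher at low exposure, which is plausible but not documented. The power figures rest on assumed concentration distributions and persister shares, and apply only if the exclusion reaches the primary model.

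**What to change.** Before database lock:

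1. In SAP 2.1.4 (Genotyping adjustment) and the 2.1.4.1 table, add a row ahead of the genotype split: LCF on or after Day 7, or LPF, with continuously positive films since baseline (no negative film) is Failure in every column, with no genotype needed.
2. For any positive film that follows at least one negative film, including where clearance was unconfirmed or was invalidated under 2.1.4.2.3, genotype the spots already collected and use the existing genotype rows. Word the trigger in Protocol 9.1.1.4 and footnote f to match.
3. State in SAP 2.3.5.1 which column of the 2.1.4.1 table the PK/PD efficacy population follows.
4. Align the populations in the Appendix B summary table with SAP 2.4.4.

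The cost is one table row, some clarifying text and possibly a few more genotyping runs on stored spots. No new sampling is needed.

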9.1.1.5 Gametocyte Detection (RT-qPCR)

Blood samples for RT-qPCR gametocyte detection will be taken according to SoA. RT-qPCR analysis will be performed by the testing laboratory at all scheduled time points to detect submicroscopic gametocytemia and characterize gametocyte maturation stage using the expression of *Pfs25* in mRNA.

9.2 ADVERSE EVENTS

Adverse event of special interest

An AESI) is an AE (serious or nonserious) of scientific and medical concern specific to the Sponsor's product or program, for which ongoing monitoring and immediate notification by the Investigator to the Sponsor is required. Such events may require further investigation in order to characterize and understand them. Adverse events of special interest may be added, modified or removed during a study by protocol amendment.

- **Pregnancy** of a female subject entered in a study as well as pregnancy occurring in a female partner of a male subject entered in a study with IMP/NIMP;
 - Pregnancy occurring in a female patient entered in the clinical trial or in a female partner of a male patient entered in the clinical trial. It will be qualified as an SAE only if it fulfills one of the seriousness criteria (see Appendix 4).
 - Follow-up of the pregnancy in a female participant or in a female partner of a male participant is mandatory until the outcome has been determined (see Appendix 5)
- **Symptomatic overdose** (serious or nonserious) with IMP/noninvestigational medicinal product (NIMP)
 - An overdose (accidental or intentional) with the IMP/NIMP is an event suspected by the Investigator or spontaneously notified by the patient (not based on systematic pills count) and defined as at least twice the intended dose.

Of note, asymptomatic overdose has to be reported as a standard AE.

• Increase in alanine transaminase (ALT)): ALT ≥3 ULN (if baseline ALT <ULN) or, ALT ≥2 times the baseline value (if baseline ALT ≥ULN) will be reported as AESI.

Cases of ALT >3 ULN will be monitored according to the procedures indicated in Appendix 7.

Patients with abnormal ALT values at Day 28 will be followed up until ALT returns to normal values. A PK sample will be made at time of event for OZ439 and FQ (& SSR97213) concentration measurement.

An ALT increase ≥ 3 ULN is reportable as an SAE in any of the following situation:

- Possible Hy's law: ALT or AST >3x ULN and bilirubin >2x ULN (>35% direct bilirubin) in the absence of a serum alkaline phosphatase level >2x ULN. [If fractionation is unavailable, record presence of detectable urinary bilirubin on dipstick indicating direct bilirubin elevations and suggesting liver injury]) or
- when ALT $>10 \times ULN$,
- when associated with jaundice or,
- when associated with coagulation disorder (prothrombin time <50%) or,
- in presence of signs of hepatic encephalopathy.
- Other project specific AESI:
 - QTcF ≥500 ms or QTcF prolongation > 60 ms from baseline

In the event of QTcF interval ≥500 ms (automatic measurement) or a QTcF prolongation >60 ms (automatic measurement) from baseline, the patient should be placed under supervision in a specialized setting.

Subsequent ECG monitoring of the patient should then be performed on a regular and clinically responsible basis until the QTc interval returns to their baseline QTcF value.

In case of QTcF ≥500 ms (automatic measurement) or QTcF prolongation >60 ms from baseline, patient will have blood drawn for measurement of OZ439 and FQ (& SSR97213) concentration.

The Investigator will report an AESI only if QTcF ≥500 ms or QTcF prolongation >60 ms from baseline is confirmed by central reading.

The definitions of an AE or SAE can be found in Appendix 4.

AE will be reported by the participant (or, when appropriate, by a caregiver, surrogate, or the participant's legally authorized representative).

The investigator and any designees are responsible for detecting, documenting, and recording events that meet the definition of an AE or SAE and remain responsible for following up AEs that are serious, considered related to the study treatment or study procedures, or that caused the participant to discontinue the study (see Section 8).

